13.4 Statistical Methods

13.4.1 General Approach

All data collected will be summarized overall and by treatment groups.

For continuous variables (e.g., age, percent diameter stenosis, and lesion length), results within treatment group will be summarized with the numbers of observations, means, medians, standard deviations, 25th and 75th percentiles, minimums, and maximums per the table mockups. Differences between the treatment groups, where specified, will be summarized with the differences of the two means, 95% confidence intervals for

the difference between the means, and p-values based on a t-test. The distributions within each group will be tested for normality using the Shapiro-Wilks test and if normality cannot be assumed then a Wilcoxon rank-sum test and 95% confidence interval of the median will be presented. The confidence interval for the difference of two means will be calculated under the assumption of unequal variances.

For categorical variables such as gender, in-hospital event rates, and angina status, results within treatment group will be summarized with patient counts and percentages. Differences between the two treatment groups, where specified, will be summarized with the difference in percentages, the asymptotic 95% confidence interval for the difference of two percentages, and a p-value based on a chi-squared test. If 20% or more of the expected cell frequencies are less than 5, a Fisher's exact test will be used to test for differences in proportions.

For the determination of event rates in-hospital, the number of all patients in the patient population will be used as the denominator. For variables ascertained at followup, the denominator will be only those patients who had follow-up performed at that time point. Unless otherwise noted, patients with missing data are excluded from the denominator.

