### 3.7 Other Secondary Endpoints

The following outcomes will be assessed between Device and Control, where appropriate:

For the Device Arm:

1. Device Success (measured at 30 days): Device is deployed as intended and the delivery system is successfully retrieved as intended at the time of the patient's exit from the cardiac catheterization laboratory (per device analysis).

THIS DOCUMENT CONTAINS CONFIDENTIAL AND PROPRIETARY INFORMATION OF EDWARDS LIFESCIENCES, LLC. IT MUST NOT BE REPRODUCED OR DISCLOSED TO THIRD PARTIES WITHOUT PRIOR WRITTEN PERMISSION OF EDWARDS LIFESCIENCES, LLC. (This template is required by ))

	2017-05 Sta	tistical Analysis Plan		8	1.0   7/16/20	19
E	Revision Date: Febr	uary 28, 2019	Rev		For Use Only by Affiliates of Edwards Lifesciences	Page 7 of 18
Edwards	Title	Statistical Analysis Plan	for	ACTIVE	2017-05	

2. Procedural Success (measured at 30 days): Device success with evidence of MR reduction  $\leq$  2+ at discharge and without the need for a surgical or percutaneous intervention prior to hospital discharge (per patient analysis).

3. Clinical Success (measured at 30 days): Procedural success with evidence of MR reduction  $\leq$  2+ and without MAEs\* at 30 days (per patient analysis).

\*Major adverse events (MAE) defined as death, stroke, myocardial infarction, pericardial effusion requiring drainage, left circumflex coronary artery injury requiring intervention, mitral valve reintervention and access site and vascular complications requiring intervention.

4. Responder analysis percentage of patients who achieve:

- a. MR  $\leq$  2+ and
- b. Meets at least two of the following criteria:
  - i. Improvement vs. baseline in symptoms (e.g., NYHA Class improvement  $\geq$  1)
  - ii. Improvement vs. baseline in functional status (6MWT improvement ≥ 30 meters)
  - iii. Improvement vs. baseline in QoL (KCCQ improvement ≥ 5 points)

For both the Device and Control Arms:

- 1. Patient success (measured at 1 year) is defined as
  - a. Patient remains alive and stroke free,
  - b. No re-hospitalizations (or equivalents) for HF, and
  - c. Patient meets at least two of the following criteria:

i. Improvement vs. baseline in symptoms (e.g., NYHA Class improvement  $\ge 1$ ) ii. Improvement vs. baseline in functional status (6MWD improvement  $\ge 30$  meters) iii. Improvement vs. baseline in QoL (KCCQ improvement  $\ge 5$  points)

2. Mean daily steps (measured at 1 year):

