### 3.9 Long Term Outcomes (Through 2, 3, 4, 5 Years)

The following outcomes will be collected yearly at 2 to 5 years:

- a. NYHA
- b. SMWT
- c. Heart failure hospitalizations
- d. Cardiovascular death
- e. Surgical mitral valve replacement or surgical repair
- f. Transcatheter based mitral valve interventions
- g. All-cause mortality
- h. Cardiac transplantation
- i. Mechanical hemodynamic support (e.g., LVAD)
- j. Number of days alive and out of hospital
- k. NT-proNBP level
- I. Need for new permanent pacemaker
- m. KCCQ
- n. SF-36

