### 6. DATA AND ANALYSIS CONVENTIONS

### 6.1 General Conventions

All data collected will be summarized overall and by treatment groups.

For continuous variables (e.g., age, percent diameter stenosis, and lesion length), results within treatment group will be summarized with the numbers of observations, means, medians, standard deviations, minimums, maximums, and 95% confidence intervals per table mockups. Differences between the treatment groups, where specified, will be summarized with the differences of the two means and 95% confidence intervals for the difference between the means, and p-values based on a t-test. The distributions within each group will be tested for normality using the Shapiro-Wilks test and if normality cannot be assumed then a Wilcoxon rank-sum test and 95% confidence interval of the median will be presented. The confidence interval for the difference of two means will be calculated under the assumption of unequal variances.

For categorical variables (e.g., gender, in-hospital event rates, and angina status), results within treatment group will be summarized with patient counts and percentages. Differences between the two treatment groups, where specified, will be

THIS DOCUMENT CONTAINS CONFIDENTIAL AND PROPRIETARY INFORMATION OF EDWARDS LIFESCIENCES, LLC. IT MUST NOT BE REPRODUCED OR DISCLOSED TO THIRD PARTIES WITHOUT PRIOR WRITTEN PERMISSION OF EDWARDS LIFESCIENCES, LLC. (This template is required by DOC ))

	2017-05 Sta	tistical Analysis Plan			1.0   7/16/20	19
	Revision Date: Febr	uary 28, 2019	Rev		For Use Only by Affiliates of Edwards Lifesciences	Page 10 of 18
Edwards	Title	Statistical Analysis Plan	for	ACTIVE	2017-05	

summarized with the difference in percentages, the asymptotic 95% confidence interval for the difference of two percentages, and a p-value based on a chi squared test. If 20% or more of the expected cell frequencies are less than 5, a Fisher's exact test will be used to test for differences in proportions.

For the determination of event rates in-hospital, the number of all patients in the patient population will be used as the denominator. For variables ascertained at follow-up, the denominator will be only those patients who had follow-up performed at that time point. Unless otherwise noted, patients with missing data are excluded from the denominator.

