### 6.2 Handling of Missing Data

No imputation of missing data will be performed. Reasonable efforts will be made to obtain complete data for all patients. Missing observations, however, will occur due to patients lost to follow-up or noncompliance with required assessments. The reasons for missing data will be evaluated (e.g. patient is deceased, lost to follow up, missed visit, etc.). In addition, the distribution of prognostic factors between patients with data and those without data will be evaluate any potential sources of bias. Any missing observations will be described in detail and evaluated for assessment of possible bias.

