### 8.3 Primary and Secondary Safety Endpoints (30 Days)

Overall rates of device and procedure related major adverse events (MAEs) though 30 days post procedure (i.e., primary safety endpoints) as well as the components will be calculated, along with 95% confidence intervals.

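### Read literally, SAP 6.1 drops patients who die before the visit from 1-year Patient success and 30-day Clinical success, although death is a failure by definition in both

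*SAP*

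**What the plan says.** SAP 6.1 sets the general denominator rule: "For variables ascertained at follow-up, the denominator will be only those patients who had follow-up performed at that time point". It adds: "Unless otherwise noted, patients with missing data are excluded from the denominator". Protocol 13.4.1 carries the same rule, under which "patients with missing data are excluded from the denominator".

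SAP 6.2 allows no imputation and counts death as a source of missingness: "The reasons for missing data will be evaluated (e.g. patient is deceased, lost to follow up, missed visit, etc". SAP 7.1 counts patients as eligible for a follow-up visit only if they are still alive before its window.

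SAP 3.7 defines two outcomes that death settles:
- Patient success at 1 year has as its first condition "Patient remains alive and stroke free". The others are no heart failure rehospitalization and improvement on at least two of NYHA class, 6MWT and KCCQ.
- Clinical success at 30 days requires Procedural success, MR of 2+ or less, and no MAE. The footnote to that definition lists death as an MAE.

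SAP 8.5 summarises the additional secondary endpoints as counts, percentages and confidence intervals. It mentions Patient success, does not list Clinical success by name, and states no denominator for any of them.

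Two other rules in SAP 6.1 deal with events. One reads: "For the determination of event rates in-hospital, the number of all patients in the patient population will be used as the denominator". The other has post-discharge results summarised by Kaplan-Meier. SAP 8.3 promises "Overall rates of device and procedure related major adverse events (MAEs) though 30 days post procedure" with 95% confidence intervals, and names neither denominator nor estimator.

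**The concern.** For both success endpoints, a death before the visit is a known outcome, namely a failure. The general rule asks instead whether the visit took place. A dead patient has no visit, SAP 6.2 classes death as a reason for missing data, and nothing is noted otherwise. A programmer who follows the text would therefore remove known failures and report a rate among survivors under a name that promises survival as a component.

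Kaplan-Meier does not repair this. Patient success needs visit-based change in NYHA, 6MWT or KCCQ, and Clinical success needs an MR grade at 30 days. Neither is a time-to-event variable.

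At stake are an inflated success rate and, for Patient success, which SAP 8.5 compares between arms, a contrast from which any mortality difference has been removed.

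**Working it through.** **The plan's own figure.** The documents give no expected value for Patient success, Clinical success or the MAE rate. The nearest closed-form figure that allows for deaths and losses is the power for co-primary endpoint 1 (SAP 8.11): 10% vs 70%, 2:1, two-sided 0.05, data for 60% of 375.
- Evaluable: 0.60 x 375 = 225, so 75 Control and 150 Device.
- Pooled proportion: (7.5 + 105)/225 = 0.50. Null SE = sqrt(0.25 x (1/75 + 1/150)) = 0.0707.
- Alternative SE = sqrt(0.09/75 + 0.21/150) = 0.0510.
- z = (0.60 - 1.96 x 0.0707)/0.0510 = 9.0, so power is above 0.999. This agrees with the stated >99%, and the present point does not touch it.

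**Patient success, one arm.** Let m be one-year mortality (20% in both groups, SAP 8.11) and s the success rate among survivors (assumed, since no document gives it). Suppose every survivor attends.
- Literal rule: s.
- Definition, with deaths as failures: s x (1 - m).
- Ratio: 1/(1 - 0.20) = 1.25.

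| s (assumed) | Literal rule | Definition | Gap |
|---|---|---|---|
| 30% | 30% | 24% | 6 points |
| 40% | 40% | 32% | 8 points |
| 50% | 50% | 40% | 10 points |
| 60% | 60% | 48% | 12 points |

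In counts, with 250 Device patients (two thirds of 375), 50 die. At s = 50% there are 100 successes, giving 100/200 = 50% against 100/250 = 40%.

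The factor depends on how many others are missing. If SAP 8.11's 60% availability, stated for the MR endpoint, also held here, and the remaining 20% were of unknown status, 50% would become 0.50 x 0.60/(0.60 + 0.20) = 37.5%, a factor of 1.33. If the synopsis's 20% attrition were all deaths, the factor is 1.25 again.

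**Patient success, between arms.** All rates below are assumed, except the plan's 20% mortality.

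| Mortality, Device / Control | s, Device / Control | Difference, literal rule | Difference, definition |
|---|---|---|---|
| 20% / 20% | 50% / 30% | 20 points | 0.400 - 0.240 = 16 points |
| 25% / 20% | 50% / 30% | 20 points | 0.375 - 0.240 = 13.5 points |
| 30% / 20% | 50% / 30% | 20 points | 0.350 - 0.240 = 11 points |
| 25% / 15% | 50% / 50% | 0 | 0.375 - 0.425 = -5 points |
| 15% / 25% | 50% / 50% | 0 | 0.425 - 0.375 = +5 points |

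The rule returns the survivors' contrast whatever the mortality. It can hide a deficit or a benefit.

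**Clinical success (Device arm only).** With 30-day mortality of 1% to 5% and success among survivors of 60% to 80% (both assumed), counting deaths as failures lowers the rate by s x m: from 0.60 x 0.01 = 0.6 points to 0.80 x 0.05 = 4.0 points.

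**The case against.** **A known death need not be missing data.** Patient success is decided once the patient dies, and SAP 6.2 can be read as explaining only why an echo, walk test or questionnaire is absent. This stands in part: the plan contains a gap, not an explicit order to drop deaths. But no sentence gives the benign reading, and SAP 6.2 and 7.1 lean the other way.

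**The consequence is limited.** Patient success and Clinical success lie outside the hierarchical family of SAP 3.6 and are only summarised descriptively. A reader might infer that the trial would conceal a mortality difference. It would not: all-cause death is the first listed component of co-primary endpoint 2 (SAP 3.3 and 8.2; that Table 1 speaks of cardiovascular death is a separate matter), all-cause mortality has a log-rank test (SAP 8.4), deaths are summarised again in SAP 9.1, and 30-day death is a secondary safety endpoint (SAP 3.5). This stands in full.

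**The primary safety rate.** A reader might infer that post-discharge deaths also drop out of the 30-day MAE rate. The documents do not support that. In-hospital event rates use all patients, post-discharge results use Kaplan-Meier, the rate runs through 30 days and is not a value ascertained at a visit, and Protocol 6.6 collects adverse events from consent to exit. What remains is that SAP 8.3 chooses none of these rules. The visit schedules place the safety primary endpoint at the 30-day visit, and the SAP's reference list cites exact binomial limits, which suit a simple proportion. The choice should not be left open.

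**Days alive and out of hospital.** A reader might extend the point to "Number of days alive and out of hospital" in SAP 3.9. Nothing ties that measure to visit attendance, and death is an input to it, so it is not part of this point.

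**Conclusion.** The point holds for 1-year Patient success and 30-day Clinical success, as a literal reading that nothing in the plan overrides. At the plan's 20% mortality, Patient success is overstated by a factor of 1.25, or 6 to 12 points for survivor success of 30% to 60%. This rests on full attendance by survivors and on assumed success rates; only the mortality comes from the documents. The effect on Clinical success is smaller, 0.6 to 4.0 points over the assumed ranges. A mortality difference between arms would not show in Patient success.

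No formal test or stated power changes, so this is a moderate correction to descriptive endpoints and does not threaten the trial's conclusions. For the 30-day MAE rate, only the missing denominator and estimator can be claimed.

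**What to change.** - **SAP 6.1 and 8.5:** state that a patient whose composite is already determined stays in the denominator as a failure whether or not the visit took place. For Patient success that means death, stroke or heart failure rehospitalization. For Clinical success it means any MAE, including death. Exclude only patients whose status is truly unknown, and report their number by arm. Name Clinical success in SAP 8.5.
- **SAP 8.3:** name the population, denominator and estimator for the 30-day MAE rate. State that the visit-performed rule does not apply and that all treated patients with an MAE count.
- **Protocol 13.4.1:** align the wording at the next update.

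This takes a few sentences and no new data. The cost is that reported success rates will be lower than under the literal rule. It should be settled before the primary-endpoint database lock, because choosing a denominator after unblinding would change the reported rates.

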Both patients were hospitalized** equal number of times	Go to Step 3
Step 3	
If no ranking yet available	
Patient in Device group but not patient in Control group	Favors Device
improved 6 minutes walking distance ≥ 40 meters compared to	
baseline	
Patient in Control group but not patient in Device group	Favors Control
improved 6 minutes walking distance ≥ 40 meters compared to	
baseline	
Both patients improved 6 minutes walking distance ≥ 40	Go to step 4
meters compared to baseline	
Neither of the patients improved 6 minutes walking distance ≥	Go to step 4
40 meters compared to baseline	
Step 4	
If no ranking yet available	
Patient in Device group (but not control) improved KCCQ score	Favors Device
≥10 points compared to baseline	
Patient in control group (but not device)improved KCCQ score	Favors Control
≥10 points compared to baseline	
Both patients improved KCCQ score ≥10 points compared to	Tie
baseline	
None of the patients improved KCCQ score ≥10 points	Tie
compared to baseline	

^{**} Only hospitalizations for heart failure are counted

The following rules are applied with the pairwise comparative outcome assessment:

- If any one of the patients in a patient pair is missing data for a variable included in the hierarchy then the pair will be considered a tie in regards to that variable/level and will proceed to the next level in the hierarchy.
- The time dependent events are censored at exactly 1 year after randomization.
- Patients who are censored during the first year (includes patients who are lost to follow-up as well as patients who die) will be compared to other patients using available data up until the time at which the patient was censored. In other words,

PROTOCOL NUMBER: 2017-05

the number of heart failure hospitalizations up until the censoring time will be compared between the patient pair.

- Inclusion of hospitalizations is based on adjudication by the Clinical Events Committee (CEC).
- The index hospitalization for Edwards Cardioband System implant in patients randomized to Device group is not counted as heart failure related hospitalization. However, if the hospital stay is prolonged beyond 5 days because of a heart failure complication, it is counted as a HF-related hospitalization. This rule is also applies to surgical mitral annuloplasty or replacement that are performed during follow-up in patients randomized to Control.

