### 5. **DEFINITIONS**

### 5.1 Analysis Dates and Days

- Study start date is defined as the procedure date.
- Last information date is defined as the most recent date assessed with any available information concerning the patient (e.g., most recent date out of: baseline assessment, procedure, discharge, follow-up visits, laboratory tests, study termination, and adverse events). Last information date is used as censor date for survival analyses.
- Study day = Date Study start date

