Survival analysis techniques will be used to analyze the time-to-event variables. Patients without events will be censored at their last known event-free time point. If this event-free time point occurs after the analysis time point, the days to event variable will be set equal to the analysis time point so that the patient will be included in the analysis. For patients who did not have an event or early withdrawal and have not yet completed the analysis visit, they will be censored at the time of their last follow-up. Time to first event curves will be constructed using Kaplan-Meier estimates and all post discharge results will be summarized with Kaplan-Meier estimates of event rates. Hazard ratios, confidence interval for the hazard ratios, and p-values may also be presented from a Cox proportional hazards model.

Covariate analyses and variables of interest, as well as possible subgroup analyses of interest, may be performed to gain more clinical insight.

Descriptive statistics will be presented at each assessment, including change from baseline to subsequent time point for selected endpoints. Paired (i.e., patients with available data at both baseline and respective time point) and unpaired data will be presented separately.

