- Patients who are censored during the first year (includes patients who are lost to follow-up as well as patients who die due to non-cardiovascular causes) will be compared to other patients using available data up until the time at which the patient was censored. In other words, the number of heart failure hospitalizations up until the censoring time will be compared between the patient pair.
- Inclusion of hospitalizations is based on adjudication by the Clinical Events Committee (CEC).
- The index hospitalization for Edwards Cardioband System implant in patients randomized to Device group is not counted as heart failure related hospitalization. However, if the hospital stay is prolonged beyond 5 days because of a heart failure (HF) complication, it is counted as a HF-related hospitalization. This rule is also applies to surgical mitral annuloplasty or replacement that is performed during follow-up in patients randomized to Control.
- Hospitalizations beginning prior to the exact 1 year time point are counted for analysis of frequency of hospitalization.

THIS DOCUMENT CONTAINS CONFIDENTIAL AND PROPRIETARY INFORMATION OF EDWARDS LIFESCIENCES, LLC. IT MUST NOT BE REPRODUCED OR DISCLOSED TO THIRD PARTIES WITHOUT PRIOR WRITTEN PERMISSION OF EDWARDS LIFESCIENCES, LLC. (This template is required by DOC))

	2017-05 Sta	tistical Analysis Plan			1.0   7/16/20	19
$\mathbb{P}$	Revision Date: Febr	uary 28, 2019	Rev		For Use Only by Affiliates of Edwards Lifesciences	Page 13 of 18
Edwards	Title	Statistical Analysis Plan for ACTIVE 2017-05				

- The 6MWT and KCCQ data from the 1-year visit are used regardless of whether the visit is before or after the exact 1 year time point.
- If clinical follow-up of one or both patients is censored, the pairwise outcome assessment is performed on the basis of those events that occurred during the smaller of the two follow-up times. For example, if a Control patient experiences an event on a particular day, and the Device patient is censored on that day or a later day, then the pair favors Device.

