### 8.11 Determination of Sample Size

Co-primary endpoint 1

Using PASS software and a test for two independent proportions 375 enrolled patients give us >99% power to detect a difference between the groups using the following assumptions:

- 1. Proportion in control arm who meet the criteria for MR reduction (MR  $\leq$  2+) is 10%.
- 2. Proportion in treatment arm who meet the criteria for MR reduction (MR  $\leq$  2+) is 70%.
- 3. A two-sided significance level (alpha) of 0.05.
- 4. A 2:1 treatment allocation ratio between Edwards Cardioband System (Device group) and control group.
- 5. Data will be available for 60% of the randomized patients (accounting for mortality and lost to follow-up).

#### Co-primary endpoint 2

Assuming up to 20% dropout, a total of 375 enrolled patients will ensure at least 300 patients with evaluable data. Based on 5,000 trial simulations using SAS software (version 9.4), it is estimated that 300 evaluable patients will provide 87% power to detect superiority of treatment vs. control using the Finkelstein-Schoenfeld test and the following assumptions:

- 1. All-cause mortality of 20% within the first year in both groups (Control and Device).
- 2. Cardiovascular mortality of 15% within the first year in both groups (Control and Device).
- 3. Number of heart failure hospitalizations within the first year:
  - a. 60% of the patients in the Control and 70% in the Device group will not have HF hospitalization.

THIS DOCUMENT CONTAINS CONFIDENTIAL AND PROPRIETARY INFORMATION OF EDWARDS LIFESCIENCES, LLC. IT MUST NOT BE REPRODUCED OR DISCLOSED TO THIRD PARTIES WITHOUT PRIOR WRITTEN PERMISSION OF EDWARDS LIFESCIENCES, LLC. (This template is required by DOC

E	Revision Date: February 28, 2019		Rev		For Use Only by Affiliates of Edwards Lifesciences	Page 17 of 18
Edwards	Title	Statistical Analysis Plan for ACTIVE 2017-05				

- b. 10% of the patients in the Control group and 10% of the patients in the Device group will have one HF hospitalization.
- c. 10% of the patients in the Control group and 5% in the Device group will have two HF hospitalizations.
- d. 10% of the patients in the Control group and 5% in the Device group will have three HF hospitalizations.
- e. 5% of the patients in the Control group and 5% in the Device group will have four HF hospitalizations.
- f. 5% of the patients in the Control group and 5% in the Device group will have five or more HF hospitalizations.

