### 9. ANALYSIS OF SAFETY

### 9.1 Deaths

Cardiovascular and all-cause death will be descriptively summarized in tables and analyzed with Kaplan-Meier estimates (depending on data sufficiency).

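### Kaplan-Meier event rates with deaths implicitly censored overstate non-fatal events and, more modestly, cardiovascular death: little at year 1, more by year 5, and only in the descriptive rates

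*SAP*

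**What the plan says.** SAP 6.1 (General Conventions) and Protocol 13.4.1 (General Approach) share the sentence that "all post discharge results will be summarized with Kaplan-Meier estimates of event rates". The same paragraph of SAP 6.1 gives the censoring rule: "Patients without events will be censored at their last known event-free time point". SAP 5.1 adds: "Last information date is used as censor date for survival analyses". SAP 9.1 states: "Cardiovascular and all-cause death will be descriptively summarized in tables and analyzed with Kaplan-Meier estimates", depending on data sufficiency.

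Neither document mentions competing risks or cumulative incidence. SAP 6.1 does not say outright that a death is a censoring event, but it gives no other treatment for a patient who dies event-free. The Finkelstein-Schoenfeld rules do class death as censoring: Protocol 13.4.2 has "includes patients who are lost to follow-up as well as patients who die" and SAP 8.2 has "patients who are lost to follow-up as well as patients who die due to non-cardiovascular causes".

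The outcomes for years 2 to 5 (SAP 3.9, Protocol 5.7) include HF hospitalization, cardiovascular death, mitral surgery or transcatheter intervention, transplantation, mechanical support and new pacemaker. SAP 8.7 and 8.8 promise only descriptive statistics and name no estimator, so the SAP 6.1 convention is the one that applies. SAP 8.11 gives the mortality assumptions: "All-cause mortality of 20% within the first year in both groups (Control and Device") and "Cardiovascular mortality of 15% within the first year in both groups (Control and Device").

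**The concern.** When deaths are censored, one minus Kaplan-Meier treats a patient who has died as still able to have the event later. It estimates the event probability in a setting without death, not the proportion of patients who have the event. With the same event and death hazards it is never below the cumulative incidence, so the direction of the error is known in advance. The gap widens as deaths accumulate, and the plan expects one patient in five to die in the first year and follows patients for five.

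At stake is how the long-term tables will be read. A reader will take a 5-year event rate as the share of patients who had the event. If mortality differed between arms, the overstatement would differ too, and the descriptive comparison would carry that difference.

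**Working it through.** The documents state no Kaplan-Meier or cumulative-incidence figure, so there is none to reproduce. The check derives both quantities from the plan's year-1 rates.

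**Inputs from SAP 8.11 (same in Protocol 13.5).** All-cause mortality 20% and cardiovascular mortality 15% in both arms; no HF hospitalization in 60% of Control and 70% of Device, so any HF hospitalization in 40% and 30%. I read the last two as cumulative incidences with death competing.

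**Assumptions not in the documents.** Constant hazards within year 1; a common factor g applied to death and event hazards after year 1 (g = 1, 1/2, 1/4); event-free patients die at the overall rate; rarer non-fatal events with 1%, 5% or 10% incidence at year 1.

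**Formulas.** With event hazard a and competing death hazard d:
- Cumulative incidence: CIF(T) = a/(a+d) × [1 − exp(−(a+d)T)]
- Planned figure: 1 − KM(T) = 1 − exp(−aT)

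Because all hazards after year 1 are scaled by the same g, year 5 is found by setting T = 1 + 4g, that is T = 5, 3 or 2.

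**Year 1.**
- Total death hazard: −ln(0.80) = 0.2231. Cardiovascular share 15/20 = 0.75, so 0.1674 cardiovascular and 0.0558 other.
- Cardiovascular death: CIF = 0.75 × 0.20 = 15.0%; 1 − KM = 1 − exp(−0.1674) = 15.4%.
- HF hospitalization, Control: CIF = 40% requires a = 0.5825 (0.5825/0.8056 × [1 − exp(−0.8056)] = 0.400); 1 − KM = 1 − exp(−0.5825) = 44.2%.
- HF hospitalization, Device: CIF = 30% requires a = 0.4038; 1 − KM = 33.2%.
- Rarer events: ratio about 1.11.

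**Year 5, CIF against 1 − KM.**

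| Event | Hazards constant (67.2% dead) | Halved after year 1 (48.8% dead) | Quartered after year 1 (36.0% dead) |
|---|---|---|---|
| Cardiovascular death | 50.4% vs 56.7% (+6.3) | 36.6% vs 39.5% (+2.9) | 27.0% vs 28.4% (+1.4) |
| HF hospitalization, Control | 71.0% vs 94.6% (+23.6) | 65.9% vs 82.6% (+16.7) | 57.9% vs 68.8% (+10.9) |
| HF hospitalization, Device | 61.6% vs 86.7% (+25.1) | 54.6% vs 70.2% (+15.6) | 46.0% vs 55.4% (+9.4) |
| Event, 10% at year 1 | 28.3% vs 44.6% (×1.57) | 22.2% vs 29.8% (×1.35) | 17.1% vs 21.0% (×1.23) |
| Event, 5% at year 1 | 15.4% vs 24.9% (×1.62) | 11.6% vs 15.8% (×1.36) | 8.8% vs 10.8% (×1.23) |
| Event, 1% at year 1 | 3.3% vs 5.5% (×1.65) | 2.4% vs 3.3% (×1.37) | 1.8% vs 2.2% (×1.24) |

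The proportion dead is 1 − 0.8^T. A simulation of 400,000 patients gave 71.1% for the Control HF cumulative incidence at year 5 with constant hazards, against 71.0% by formula.

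**Additivity.** With constant hazards at year 5, 1 − KM for cardiovascular death (56.7%) plus 1 − KM for other death (1 − exp(−0.0558 × 5) = 24.3%) is 81.0%, while all-cause mortality is 67.2%. Cumulative incidences for the two causes add up to all-cause mortality; Kaplan-Meier figures do not.

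**The case against.** The strongest objection is that this changes no conclusion. Co-primary endpoint 1 is a chi-square test and co-primary endpoint 2 is Finkelstein-Schoenfeld. The key secondary analyses of HF hospitalization (Andersen-Gill) and of mortality (log-rank) do not use these rates. That stands in full.

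Kaplan-Meier is also not the only display. Deaths are tabulated, adverse events are given as patient and event counts (SAP 9.2), and all-cause mortality is reported alongside. A careful reader could notice the discrepancy, but the headline rate would still be wrong.

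A reader might infer that the plan's own mortality produces a heavy overstatement at year 5. The documents do not support that: 20% and 15% are one-year figures, and the constant-hazard column is the largest of the three scenarios. Nor is the year-5 gap heavy for cardiovascular death, because only the smaller non-cardiovascular part of mortality competes. If deaths cluster after HF hospitalization, event-free patients die at less than the overall rate and the HF gap shrinks.

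A reader might also infer a distorted comparison between arms. The plan assumes equal mortality, and the Control-minus-Device difference in HF hospitalization is then 10.9 points by Kaplan-Meier against 10.0 at year 1, and 7.8 against 9.4 at year 5 with constant hazards. Distortion through unequal mortality is possible but is not something the plan predicts. As illustration only, an event hazard of 0.05 per year in both arms gives 22.1% by Kaplan-Meier at 5 years in each, while the cumulative incidence is 17.4% at 10% annual mortality and 13.6% at 20%.

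Finally, stroke should not be counted as a 5-year outcome without qualification. Protocol 5.8 and SAP 3.10 end stroke, TIA, vascular and renal outcomes at 1 year; only the heading of SAP 8.8 says 5 years.

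**Conclusion.** The point holds for descriptive event rates. Followed as written, the plan overstates the probability of every post-discharge event other than all-cause death and composites that include it. The direction is certain once deaths are censored, and censoring at death is the only reading that SAP 6.1 and 5.1 leave open, though it is implied and not stated.

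At year 1 the excess is small: 0.4 points for cardiovascular death and 3 to 4 points for HF hospitalization. At year 5 it is moderate for cardiovascular death (about 1.4 to 6.3 points), large for HF hospitalization (about 11 to 24 points in Control, 9 to 25 in Device), and a factor of about 1.23 to 1.65 for rarer non-fatal events. Stroke, TIA, vascular and renal outcomes are overstated by a factor of about 1.11 if they end at year 1.

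The year-1 sizes rest on the plan's rates, on constant hazards within the year, and on reading the HF percentages as cumulative incidences. The year-5 sizes rest also on hazards that the documents do not give, and should be quoted only as a range. The correction is worth making before analysis; it does not call the confirmatory results into question.

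**What to change.** In SAP 6.1 and 9.1:
- Keep Kaplan-Meier for all-cause death and for composites that include it.
- Report non-fatal events as Aalen-Johansen cumulative incidence, with death from any cause as the competing event.
- Report cardiovascular death as cumulative incidence, with non-cardiovascular death as the competing event.
- State explicitly how a patient who dies event-free is handled.

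Make the same change in Protocol 13.4.1, or declare it in SAP section 10, which at present lists only the roll-in enrolled population as a difference from the protocol. Reconcile the 1-year and 5-year headings for the long-term safety outcomes (SAP 3.10 and Protocol 5.8 against SAP 8.8). The log-rank, Cox and Andersen-Gill analyses can stay as they are.

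The cost is a little more programming with standard software, a matching document change, and lower reported rates. No new data, visits or patients are needed.
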